3.10 Missing data and other data issues

3.10.1 Missing data

For vestibular pain using a vaginal dilator, if a dilator size is not tested due to pain intensity, the pain will be scored at 10. If the test is not done due to other reasons, then the pain score will be considered as missing.

When calculating the composite score for the vaginal dilator induced pain and dilator size, there should be at least 6 pain scores (recorded by the investigator) to calculate the composite score. When missing, pain score will be imputed by the average of the previous (smaller dilator size) and the following (larger dilator size) valid values. For example, if the pain score for dilator size 4 is missing, then it will be imputed by the average of the pains scores for dilator size 3 and size 5 when both of them are available.

For mVPAQ, Pain Severity should have at least 4 (out of 6) valid inputs; Emotional Response should have at least 10 (out of 15) valid inputs; Cognitive Response should have at least 5 (out of 8) valid inputs; Life Interference should have at least 7 (out of 11) valid inputs; Sexual Function Interference should have at least 7 (out of 10) valid inputs; Self-Stimulation/Penetration Interference should have at least 3 (out of 5) valid inputs. The not applicable “N/A” entries are considered as valid inputs.

For mFSFI, Desire domain should have at least 2 (out of 2) valid inputs; Arousal and Lubrication domains should have at least 3 (out of 4) valid inputs; Orgasm, satisfaction and Pain domains should have at least 2 (out of 3) valid inputs. There should be at least 4 (out of 6) non missing domain scores to calculate the total score.

For PHQ-9, there should be at least 6 (out of 9) valid inputs to calculate the total score. When calculating scores/subscale scores from questionnaires (e.g, mVPAQ mFSFI, and PHQ-9), the missing item value will be ignored, and the scores computed will be scaled to have the same possible maximum score as for the whole questionnaire (by dividing the possible maximum score based on questions with non-missing values and multiplying the possible maximum score for the whole questionnaire).

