#### 4.2 Exclusion Criteria

Subjects will not be included in the study if they meet any of the following exclusion criteria:

- (1a) Have provoked pain on a Q-tip test at the anterior vestibule (anywhere between 9 and 3 o'clock or more anteriorly) at the Screening Visit.
- (2b) Able to tolerate the 6th (diameter 1½ inches) dilator size (i.e. agree to the next successive dilator size to be tested for pain response) at the Baseline Visit (i.e. at least one of the two largest sized dilators (#7 and/or 8) is tested).
- (3a) Any non-provoked (i.e. spontaneous) vulvar pain in the past 6 months prior to the Screening Visit. Note: pain provoked by any vestibular pressure (including but not limited to sitting, bicycling or tight clothing) is considered provoked pain.
- (4a) Deep pain during intercourse in the past 6 months prior to the Screening Visit.
- (5a) Score of 4 or 5 on any of the 3 pain questions (questions #17, 18 or 19) of the mFSFI questionnaire.
- (6) *Criterion 6 is removed by previous protocol amendment.*
- (7a) Significant depressive disorder, e.g. having a score  $\geq 20/27$  on the Patient Health Questionnaire (PHQ-9) scale at the Baseline Visit.
- (8b) Genitourinary or gastrointestinal conditions/history including:
  - Skin disease at the vestibule such as lichen sclerosus, lichen planus, vaginal or vulvar atrophy, desquamative inflammatory vaginitis and allergic vulvitis.
  - Severe endometriosis (severe defined as requiring regular medications to manage the endometriosis symptoms).
  - Severe bladder and bowel symptoms e.g. diagnosed interstitial cystitis/Bladder Pain Syndrome, severe urinary incontinence, faecal incontinence, inflammatory bowel disease.
  - Genitourinary or rectal cancer.
  - Congenital urogenital abnormalities (e.g. vaginal septa, imperforate hymen, urethral diverticulum).
  - Pain in urethra (diagnosis based on subject's interview and physical examination).
  - Symptomatic urogenital prolapse at physical examination.
  - History of traumatic or post radiotherapy vulvar lesions.
  - Pudendal neuralgia
  - Other conditions that in accordance to the investigator's judgement may interfere with treatment or impact the study outcome.
- (9) Previous surgery/conditions including:
  - Hysterectomy
  - Vestibulectomy
  - Urologic surgery
  - Perianal surgery
  - Genital trauma or mutilation/cutting
  - Other surgery/conditions that according to the investigator's judgement may impact the study outcome

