## 5.2 Study Visits

For the purpose of study visits and procedures, the duration of 1 month=4 weeks=28 days. For assessments done at the Screening Visit, but not repeated at the Baseline Visit, the Screening values will be considered as Baseline.

Subjects are required to remain at the clinic for the required duration of study assessments and for at least 30 minutes after study drug administration.

The priority order for performing the assessments is discussed in Section 6.6.

If the COVID-19 pandemic prevents subjects from coming to the site, study assessments planned in the protocol will be limited to the ones possible remotely, denoted with an asterisk (\*) in Table 2, Table 3, Section 5.2.2, Section 5.2.3 and Section 5.2.4; of note no study assessments should be performed remotely for the Screening, Baseline and EOS/EWD visits. Completion of questionnaires on the subjects' own device will be performed provided that the site staff can access the ePRO system to record the visit date.

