**Table 8 Secondary Efficacy Endpoints and Evaluations**

Measure	Timepoint	Variable	Endpoint
Vestibular pain using a vaginal dilator	Screening, Baseline, Week 6, Week 12 and then every 6 weeks until EOS - All TCs	11-point NRS score for each dilator size that is tolerated by the subject	Mean change from Baseline in the vaginal dilator induced pain (using the DMTS reported at baseline)
			Proportion of subjects who reported at least 30% decrease from Baseline in the vaginal dilator induced pain using DMTS at Baseline
			Proportion of subjects who reported at least 2-point decrease from Baseline in the vaginal dilator induced pain using DMTS at Baseline
			Proportion of subjects who reported at least 50% decrease in vaginal dilator induced pain using the DMTS at Baseline
Maximum tested dilator size	Screening, Baseline, Week 6, Week 12 and then every 6 weeks until EOS - All TCs	Dilator size	Mean change from Baseline in the dilator size that provokes maximum tolerated pain
Composite of vestibular pain induced by the dilator and the tolerability of the dilator size	Screening, Baseline, Week 6, Week 12 and then every 6 weeks until EOS - All TCs	Composite score of 11-point NRS score and dilator size	Mean change from Baseline in the composite score for vaginal dilator induced pain and dilator size. The composite score is the sum of all pain measurements across the full range of dilator sizes. In the construction of this endpoint, the pain score will be 10 for any dilator size that is not tested because it is beyond tolerability.
Frequency of intercourse and pain during intercourse [a]	Screening, Baseline, Week 6, Week 12 and then every 6 weeks until EOS - All TCs	11-point NRS score	Mean change from Baseline in the frequency of intercourse and pain during intercourse

Measure	Timepoint	Variable	Endpoint
Pain during insertion of vaginal dilator number 6 size [b]	Screening, Baseline, Week 6, Week 12 and then every 6 weeks until EOS - All TCs	11-point NRS score	Mean change from Baseline in pain during insertion
			Proportion of subjects having reported at least a 30% decrease in pain during insertion on the mean of the NRS values
			Proportion of subjects having reported at least a 50% decrease in pain during insertion on the mean of the NRS values
			Proportion of subjects having reported at least 2-point decrease in on the mean of the NRS values.

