### 7.4.1 *Dilator Test (Vaginal Dilator Induced Pain)*

A set of 8 vaginal dilators of increasing diameter (#1 being the smallest and #8 being the largest) will be used to provoke pain to allow assessment of the vestibular pain intensity in each subject. At each visit, the investigator will insert the dilator between 3 to 4 cm depth in the vagina starting with the smallest sized dilator and progressively increasing the size of the dilator. No lubricant, other than water, may be used when inserting the dilator. In order to standardise the methodology each dilator should be inserted for a period of 5 to 10 seconds and the time period between the insertion of two dilators should be 30 seconds to 1 minute. Subjects will be required to rate the pain for each dilator size on an 11-point NRS ([Figure 4](#)) at each visit. Based on the subjective pain threshold, the largest sized dilator that the subject accepts/tolerates for the test (i.e. does not agree to the next successive dilator size to be tested), will be defined as the Dilator Maximum Tested Size (DMTS) that will be established at Baseline Visit. The dilator test will be used to assess the change from Baseline in the vaginal dilator induced pain as reported on a NRS (using the DMTS reported at baseline) as well as the dilator size that provokes maximum tolerated pain.

**Figure 4** Numeric Pain Rating Scale

Subject interviews to assess the content relevance of the dilator test will be performed in Stage 2. Subjects from Stage 2 will be invited to complete the interview until the target sample of 20 subjects is achieved. Every effort should be made to conduct the interview within 2 weeks of the subject's Cycle 1-Week 6 visit.

The subject interviews will be conducted by experienced interviewers trained in qualitative interview techniques. The details of the interview will be provided in the interview guide.

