No control of the overall type I error rate is planned as only exploratory descriptive statistics are planned.

2 **SUBJECT POPULATIONS (ANALYSIS SETS)**

Screened population

The screened population is all subjects screened (i.e. who signed the informed consent).

Randomized population

Randomized population is all subjects randomized (i.e. who were randomly allocated to a treatment group).

modified Intent-To-Treat population

The modified Intent-to-Treat (mITT) population is all randomized subjects who received at least one IMP administration and had data for the vaginal dilator induced pain as reported on an 11-point NRS [using the Dilator Maximum Tested Size (DMTS) reported at Baseline] at Baseline and Cycle 1-Week 6 visit (i.e. at least one pain score for one dilator size, which enables an imputed pain score of 10 at DMTS if needed).

The mITT population will be analyzed using subjects as randomized.

Active Treatment Population

The Active Treatment Population is all randomized subjects who received at least one dose of Dysport (including only partial administration) during the DB and/or OL period.

Safety

The safety population is all randomized subjects who received at least one dose of IMP administration (including only partial administration).

The safety population will be analyzed using subjects as treated (i.e. according to actual treatment received).

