visit (repeat for 30% decrease)	Active Treatment Cycle: - A summary by number of active treatment cycles will be used.
Proportion of subjects who reported at least 2-point decrease from baseline in vaginal dilator pain as reported on the 11-point NRS[1] at each post-treatment visit	
 - descriptive statistics: actual values and change from baseline values will be presented at all timepoints. - Number and percentage of each size will be provided at all timepoints. 
Active Treatment Cycle:
 
 - A summary by number of active treatment cycles will be used.
Mean change from Baseline to each post-treatment visit in the dilator size that provokes maximum tolerated pain	
Composite score derivation:
 
The composite score for the vaginal dilator induced pain and dilator size is the sum of all pain measurements across the full range of dilator sizes. In the construction of this endpoint, the pain score will be 10 for any dilator size that is beyond the DTMS. As described in section 3.10.1, there should be at least 6 pain scores (recorded by the investigator) to calculate the composite score. When there is a dilator size score missing, pain score will be imputed by the average of the previous (smaller dilator size) and the following (larger dilator size) valid values. For example, if the pain score for dilator size 4 is missing, then it will be imputed by the average of the pain scores for dilator size 3 and size 5 when both of them are available.
 
 - descriptive statistics: actual values and change from baseline values will be presented at all timepoints. 
Active Treatment Cycle:
 
 - A summary by number of active treatment cycles will be used.

[1] Using DTMS at baseline.

Pain during insertion of vaginal dilator number 6 size

Cohort 1: once a week during the Screening period (Day -14 to Day 1), and once a week during the month (28 days) prior to the next planned visit, all subjects are to rate pain following insertion of the number 6 vaginal dilator (11-point NRS) and to record details of associated pain medication if consumed. Data are recorded in the patient's eDiary.

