3.11 Derived data

The derived data are variables which are calculated from the raw data in the eCRF and not included in the database.

The following derived data will be calculated and included in the listings:

(1) Age

Subject age (years) will be derived as (screening year – birth year).

(2) BMI

BMI (kg/m^2) will be derived as $\text{Weight}(\text{kg})/[\text{Height}(\text{cm})/100]^2$.

(3) Changes from Baseline

Changes from Baseline will be calculated as a difference from Baseline (e.g. assessment at the visit – assessment at Baseline).

(4) Adverse event duration

The AE duration = AE end date - AE start date + 1. If the start and end dates of the adverse event are identical then “ <1 ” day will be presented, otherwise, it will be calculated as (end date - start date)+1 and presented in days. If the recorded end date is CONT. (for continuing), the end date will be listed as “ongoing” and the duration will be approximated as “ $\geq(\text{last attended visit date} - \text{start date})+1$ ” day(s). If the start date or the end date are partial the duration will be presented as a superior inequality “ $\geq xx$ ” day(s) [i.e.: ≥ 2 where start date=31JAN2004 and end date=FEB2004 or start date=JAN2004 and end date=01FEB2004].

(5) Concomitant therapy duration

The duration of concomitant treatments/physiotherapy etc. will be calculated as (end date - start date) +1. If the recorded end date is CONT. (for continuing) then the end date will be listed as “ongoing” and the duration will be approximated as “ $\geq(\text{last attended visit date} - \text{start date})+1$ ” day(s). If the start date or the end date are partial, the duration will be presented as an inequality “ $\geq xx$ ” day(s) [i.e.: ≥ 2 where start date=31JAN2004 and end date=FEB2004 or start date=JAN2004 and end date=01FEB2004] but if both are partial or one is missing the duration will not be presented.

(6) Study day

Study day will be defined as ‘-1’ for the day prior to first study drug administration and as ‘1’ for the day of first study drug administration (i.e. day 0 does not exist).

(7) Study Baseline

Baseline is defined as the last value, or the derived value specified for the parameter, available prior to the first study IMP treatment administration (i.e. prior to the DB period). Baseline for the active dysport cycle analysis will be the same as Baseline for the DB period, i.e., Baseline of the first study cycle.

(8) Treatment cycle day

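### As worded, the six-score minimum makes the composite dilator score computable at the Baseline Visit only when the maximum tested size is exactly 6

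*SAP*

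**What the plan says.** The composite adds the pain scores over all eight dilator sizes. Protocol Table 8 states that "the pain score will be 10 for any dilator size that is not tested because it is beyond tolerability" and sets no minimum number of scores. SAP Section 3.8.2, Table 1, has the corresponding rule: "the pain score will be 10 for any dilator size that is beyond the DTMS".

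The SAP then adds a minimum, in Table 1 and again in Section 3.10.1: "there should be at least 6 pain scores (recorded by the investigator) to calculate the composite score". A size missing between two scored sizes is filled with the average of its neighbours; the worked example fills size 4 from sizes 3 and 5.

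Two protocol provisions limit how many scores can be recorded. In Section 7.4.1 the test proceeds "starting with the smallest sized dilator and progressively increasing the size of the dilator", until the subject declines the next size. In Section 4.2, exclusion criterion 2b excludes a subject who tolerates size 6 at the Baseline Visit, explained as meaning that "at least one of the two largest sized dilators (#7 and/or 8) is tested".

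**The concern.** The minimum and the score-10 construction work against each other. The 10s exist so that a subject who stops early still has a full set of eight values. A minimum restricted to scores the investigator recorded removes the subjects for whom the 10s were introduced.

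Change from Baseline in the composite is a secondary endpoint (Protocol Section 3.2.2). SAP Section 3.11 uses the same Baseline for the active treatment cycle analyses, so a subject without a Baseline composite has no change score at any visit or cycle. The rule also applies after treatment. A subject who goes from size 6 to size 5 would drop out of the composite analysis instead of contributing a score, so missingness would depend on outcome.

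**Working it through.** The six is a chosen threshold with no figure behind it to reproduce, so the check is an enumeration.

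**Inputs**
- Number of sizes: 8 (Protocol Section 7.4.1).
- Order: ascending from size 1. With no gaps, recorded scores = d, where d is the largest size tested at the visit.
- Sizes scored 10 = 8 − d (Protocol Table 8; SAP Table 1).
- Eligible d at the Baseline Visit: 1 to 6 (exclusion 2b). Inclusion 9a requires sizes 1 and 2 to be tested at Screening, but no lower limit is stated for the Baseline Visit.
- Minimum: 6.

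**Baseline Visit**

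| d | Recorded | Scored 10 | Total values | Recorded ≥ 6? | Total ≥ 6? |
|---|---|---|---|---|---|
| 1 | 1 | 7 | 8 | no | yes |
| 2 | 2 | 6 | 8 | no | yes |
| 3 | 3 | 5 | 8 | no | yes |
| 4 | 4 | 4 | 8 | no | yes |
| 5 | 5 | 3 | 8 | no | yes |
| 6 | 6 | 2 | 8 | yes | yes |

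On the literal rule 1 of the 6 possible DMTS values passes, and only with no gap: at d = 6, one missing score leaves 5. If the 10s count, every value passes, and up to two of the eight sizes can be missing for other reasons (8 − 2 = 6).

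**Change from Baseline, without Screening values**

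The literal rule needs d ≥ 6 at both visits. There are 6 × 8 = 48 pairs of Baseline d (1 to 6) and later d (1 to 8).
- Smaller later size: 0 + 1 + 2 + 3 + 4 + 5 = 15 pairs; 0 pass.
- Same size: 6 pairs; 1 passes (6 to 6).
- Larger later size: 7 + 6 + 5 + 4 + 3 + 2 = 27 pairs; 2 pass (6 to 7 and 6 to 8).
- Total: 3 of 48. If the 10s count, 48 of 48.

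**The SAP's own interpolation example, at Baseline**

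Size 4 is missing and size 5 was tested and scored, so d is 5 or 6. Recorded scores are 5 − 1 = 4 or 6 − 1 = 5, both below 6, so the composite is not computed and the interpolation never operates. With the 10s there are 8 − 1 = 7 values and it works.

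**Number of subjects**

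The documents give no DMTS distribution, so the loss cannot be stated. As an assumption only: Cohorts 1 to 6 were planned at 5 × 10 + 8 = 58 evaluable subjects. If 5% to 50% of them had DMTS 6, then 58 × 0.05 = 2.9 to 58 × 0.50 = 29 would have a Baseline Visit composite under the literal rule.

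**Can a Screening value stand in?**

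SAP Section 3.11 states: "Baseline is defined as the last value, or the derived value specified for the parameter, available prior to the first study IMP treatment administration". That might let in a Screening composite, since exclusion 2b does not cap the size tested at Screening. Protocol Section 5.2 points the other way: "For assessments done at the Screening Visit, but not repeated at the Baseline Visit, the Screening values will be considered as Baseline". The dilator test is repeated at the Baseline Visit (Section 5.2.2.1). Carrying in Screening would in any case not help a subject with fewer than six sizes tested at both visits.

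**The case against.** The strongest reply is that the literal reading is not the intended one. Section 3.10.1 first assigns 10 to sizes stopped by pain and treats only other untested sizes as missing; the minimum comes after that. Six of eight (75%) is in line with most of the questionnaire minimums in the same section, such as 4 of 6 or 6 of 9. The literal reading disables the SAP's own example at Baseline. The parenthesis may only identify the source: clinic scores are entered in the eCRF by the investigator or site staff, whereas home insertion of size 6 goes into the eDiary.

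Much of this stands as evidence of intent, and the 10s were probably meant to count. It does not settle the text. No passage says that the 10s count or that the site enters a 10 for an untested size. In defining the mITT population (SAP Section 2), the plan calls the 10 imputed: "at least one pain score for one dilator size, which enables an imputed pain score of 10 at DMTS if needed". The questionnaire minimums ask for valid inputs; only this one specifies who recorded the score. Two programmers could follow the same SAP and report very different numbers of subjects.

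Two further objections limit the consequences. A fall in tolerated size is captured elsewhere: change in dilator size is its own secondary endpoint, and a subject who cannot reach her Baseline DMTS because of pain scores 10 on the DMTS pain endpoint. And 3 of 48 weights all combinations equally, including Baseline size 1, so it must not be read as a proportion of subjects.

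**Conclusion.** The rule is wrong as written. Taken literally it gives a Baseline Visit composite only at DMTS 6 with all six scores present, and a change score in 3 of 48 size combinations, none with a smaller later size. Within the composite, worsening in size would never be captured.

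This rests on ascending testing without gaps, on compliance with exclusion 2b (a subject enrolled in breach of it could pass), and on Screening values not being carried in. The share of subjects affected is unknown.

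The consequence is limited. The endpoint is secondary and descriptive, the study stopped before Stage 2, and neither a hypothesis test nor the sample size depends on it. DMTS pain and dilator size do not use the rule. It should still be corrected, because the present wording can empty a protocol endpoint that needs no such restriction.

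**What to change.** In SAP Table 1 (Section 3.8.2) and Section 3.10.1, replace the minimum with: the composite is calculated if at least 6 of the 8 sizes have a value after sizes not tested because of pain have been scored 10; only sizes not tested for other reasons count as missing and are interpolated.

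This agrees with Protocol Table 8, makes the size-4 example work at Baseline, and restores the composite for every DMTS. It costs one sentence in two places, needs no new data, and should be settled before database lock.

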3.10.2 Missing or incomplete dates

In all listings, missing or incomplete dates should be left as they have been recorded. However, for calculation / sorting / assignation based on dates, the following methods will be used:

The most conservative approach will be systematically considered (i.e. if the onset date of an AE/concomitant medication is missing / incomplete, it is assumed to have occurred during the study treatment phase (i.e. a TEAE for AEs) except if the partial onset date or other data [stop date, ...] indicates differently).

- A missing/incomplete date of medical history or disease diagnosis will be assumed to have occurred before any study treatment,
- A medication with partial start and stop dates will be considered as concomitant treatment, except if the partial dates indicate differently,
- If an AE or SAE onset date is partial or missing, the event will be allocated to the first treatment where onset could have occurred (taking into account date and time stopped),
- If the start date of a medication is partial or missing, the medication will be assigned to the most recent treatment received on or before the medication start date (taking into account date stopped).

Where this is possible, the derivations based on a partial date will be presented as superior inequalities (i.e.: for an AE started in FEB2004 after the administration performed on 31JAN2004, the days since last dose will be “ ≥ 2 ”, similarly the duration of ongoing AEs or medication will be “ $\geq xx$ ” according to the start and last visit dates).

If the date of diagnosis for provoked vestibulodynia is partial, the duration of provoked vestibulodynia will be calculated as follow: 1) If only day is missing, only month and year will be used in calculation. 2) If month is missing, only year will be used in calculation. 3) No imputation should be done at the data level.

